6.7 Emergency breaking of assigned treatment code

Emergency code breaks must only be undertaken when it is required to in order to treat the patient safely. Most often, study treatment discontinuation and knowledge of the possible treatment assignments are sufficient to treat a study patient who presents with an emergency condition. Emergency treatment code breaks are performed using the IRT. When the investigator contacts the system to break a treatment code for a patient, he/she must provide the requested patient identifying information and confirm the necessity to break the treatment code for the patient. The investigator will then receive details of the investigational drug treatment for the specified patient and a fax or email confirming this information. The system will automatically inform the study monitor for the site and the Study Team that the code has been broken.

It is the investigator's responsibility to ensure that there is a dependable procedure in place to allow access to the IRT at any time in case of emergency. The investigator will need to provide:

- protocol number
- study drug name (if available)
- patient number

In addition, the investigator must provide information to inform the patient how to contact his/her backup in cases of emergency when he/she is unavailable to ensure that un-blinding can be performed at any time.

An assessment will be done by the appropriate site personnel and sponsor after an emergency unblinding to assess whether or not study treatment should be discontinued for a given patient and whether the patient can continue in the study.

6.8 Treatment exposure and compliance

Pharmacokinetic parameters (measures of treatment exposure) will be determined in all patients treated with LMB763, as detailed in [Section 8.7](#).

The investigator must promote compliance by instructing the patient to take the study treatment exactly as prescribed and by stating that compliance is necessary for the patient's safety and the validity of the study. The patient must also be instructed to contact the investigator if he/she is unable for any reason to take the study treatment as prescribed.

Compliance will be assessed by the Investigator and/or study personnel at each visit using pill counts and information provided by the patient. This information should be captured in the source document at each visit. All study treatment dispensed and returned must be recorded in the Drug Accountability Log.

6.9 Recommended treatment of adverse events

Treatment of AEs may be considered at the discretion of the Investigator. Medication used to treat AEs must be recorded on the Concomitant medications/Significant non-drug therapies CRF.

6.10 Rescue medication

Use of rescue medication is not allowed during the study.

6.11 Concomitant treatment

All prescription medications, over-the-counter drugs and significant non-drug therapies (including physical therapy and blood transfusions) administered or taken within the timeframe defined in the entry criteria prior to the start of the study and during the study, must be recorded on the Concomitant Medications/Significant non-drug therapies section of the CRF.

Medication entries should be specific to trade name, the single dose and unit, the frequency and route of administration, the start and discontinuation date and the reason for therapy.

7 Study completion and discontinuation

7.1 Study completion and post-study treatment

Each patient will be required to complete the study in its entirety and thereafter no further study treatment will be made available to them.

Study completion is defined as when the last patient completes their Study Completion visit, and any repeat assessments associated with this visit have been documented and followed-up appropriately by the Investigator, or in the event of an early study termination decision, the date of that decision.

All patients should have a safety follow-up call conducted 30 days after last visit. The information collected is kept as source documentation. All SAEs reported during this time period must be reported as described in [Section 9.2](#) and the Site Operations Manual. Documentation of attempts to contact the patient should be recorded in the source documentation.

7.2 Discontinuation of study treatment

Patients may voluntarily discontinue study treatment for any reason at any time.

The investigator must discontinue study treatment for a given patient if, on balance, he/she believes that continuation would be detrimental to the patient's well-being.

Individual patient withdrawal:

Patients may voluntarily withdraw from the study for any reason at any time. They may be considered withdrawn if they state an intention to withdraw, fail to return for visits, or become lost to follow-up for any other reason. If a patient withdrawal occurs for any reason, the Investigator must make every effort to determine the primary reason for a patient's withdrawal from the study and record this information on the Study Completion CRF.

Individual treatment discontinuation:

Study treatment must be discontinued and the patient withdrawn from the study if the patient withdraws consent.

Study treatment must be discontinued if the following occur:

- Pregnancy.
- Hypersensitivity (CTCAE grade 2 or higher) reaction to LMB763 requiring intervention.
- Adverse events, abnormal laboratory values or abnormal test result that indicate a safety risk to the patient, in the opinion of the investigator
- An adverse event that is a CTCAE Grade 3 and believed to be related to the study drug (apart from liver and renal events - see below).
- A liver safety event as defined in [Section 9.3](#) (Liver safety monitoring) with ALT, AST, total bilirubin and/or alkaline phosphatase elevations mandating study treatment discontinuation. Please refer to [Section 9.3](#) (Liver safety monitoring), [Table 9-1](#) and [Table 9-2](#) for further instructions and monitoring.
- A renal safety event as defined in [Section 9.4](#) with serum creatinine elevations mandating study treatment discontinuation. Please refer to [Section 9.4](#) for further instructions and monitoring.
- Any protocol deviation that results in a significant risk to the patient's safety in the opinion of the investigator.
- If continuation in the study is deemed detrimental to the patient's well-being in the opinion of the investigator.

The appropriate personnel from the study site and Novartis (including the CTT, medically qualified representatives of the Sponsor, and the investigator) will assess whether study treatment should be discontinued for any patient whose treatment code has been broken inadvertently for any reason.

Patients who discontinue study treatment or who decide they do not wish to participate in the study further should NOT be considered withdrawn from the study UNLESS they withdraw their consent. Where possible, they should return for follow up assessments at the end of study visit. If they fail to return for assessments for unknown reasons, every effort (e.g. telephone, e-mail, letter) should be made to contact them.

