All follow-up information, and the procedures performed must be recorded as appropriate in the CRF.

Table 9-2 Actions required for Liver Events

Criteria	Actions required	Follow-up monitoring
Potential Hy's Law case ^a	
 • Discontinue the study drug immediately • Hospitalize, if clinically appropriate • Establish causality 	ALT, AST, TBL, Alb, PT/INR, ALP and GGT until resolution ^c (frequency at investigator discretion)
ALT or AST		
$> 8 \times$ ULN and $> 2 \times$ baseline value	
 • Discontinue the study drug immediately • Hospitalize if clinically appropriate • Establish causality 	ALT, AST, TBL, Alb, PT/INR, ALP and GGT until resolution ^c (frequency at investigator discretion)
$> 3 \times$ ULN and $> 2 \times$ baseline value and INR > 1.5	
 • Discontinue the study drug immediately • Hospitalize, if clinically appropriate • Establish causality 	ALT, AST, TBL, Alb, PT/INR, ALP and GGT until resolution ^c (frequency at investigator discretion)
$> 5 \times$ ULN and $> 2 \times$ baseline value but $\leq 8 \times$ ULN	
 • Repeat LFT within 48 hours • If elevation is confirmed, refer to Table 6-3 	Refer to Table 6-3 ALT, AST, TBL, Alb, PT/INR, ALP and GGT until resolution ^c (frequency at investigator discretion)
$> 3 \times$ ULN and $> 2 \times$ baseline value, accompanied by symptoms ^b	
 • Discontinue the study drug immediately • Hospitalize if clinically appropriate • Establish causality 	Refer to Table 6-3 ALT, AST, TBL, Alb, PT/INR, ALP and GGT until resolution ^c (frequency at investigator discretion)

Criteria	Actions required	Follow-up monitoring
> 3 to ≤ 5 × ULN if normal baseline or >2 × baseline if elevated before drug exposure (patient is asymptomatic)	
 Repeat LFT within 48-72 hours If elevation is confirmed, refer to Table 6-3 	
Refer to Table 6-3
 
Investigator discretion

ALP (isolated)		
> 2 × ULN if normal baseline (in the absence of known bone pathology)	
 Repeat LFT within 48 hours If elevation persists, establish causality Complete liver CRF 	
Investigator discretion
 
Monitor LFT within 1 to 4 weeks or at next visit

TBL (isolated)		

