9.4 Renal safety monitoring

Every renal laboratory trigger or renal event must be followed up by the investigator or designated personnel at the trial site. Recommended actions and follow-up assessments are listed in [Table 9-4](#) and [Table 9-5](#), respectively.

Table 9-4 Specific Renal Alert Criteria and Actions

Renal Event	Actions
Serum creatinine increase 25 – 49% compared to baseline	
Confirm 25% increase after 24-48h
 
Follow up within 2-5 days

Serum creatinine increase $\geq 50\%$ compared to baseline	
Confirm $\geq 50\%$ within 24-48 hours after receipt of the abnormal value
 
If confirmation of abnormal value is not possible in this timeframe study drug must be withheld until further evaluation is possible
 
Consider drug interruption
 
Consider patient hospitalization / specialized treatment

Albumin- or Protein-creatinine ratio increase ≥ 2 -fold	
Confirm value after 24-48h
 
Perform urine microscopy

Albumin-creatinine ratio (ACR) ≥ 30 mg/g or ≥ 3 mg/mmol; New dipstick proteinuria $\geq 1+$	
Consider drug interruption / discontinuation

Protein-creatinine ratio (PCR) ≥ 150 mg/g or ≥ 15 mg/mmol	
New dipstick glucosuria $\geq 1+$ not due to diabetes	
Blood glucose (fasting)
 
Perform serum creatinine, ACR

New dipstick hematuria not due to trauma	
Urine sediment microscopy
 
Perform serum creatinine, ACR

Additional specialized assessments are available to assess renal function or renal pathology. (Note: In exceptional cases when a nephrologist considers a renal biopsy, it is strongly recommended to make specimen slides available for evaluation by Novartis to potentially identify project-wide patterns of nephrotoxicity.)

Whenever a renal event is identified, a detailed patient history and examination are indicated to identify, document and potentially eliminate risk factors that may have initiated or contributed to the event:

- Blood pressure assessment (after 5 min rest, with an appropriate cuff size)
- Signs and symptoms such as fever, headache, shortness of breath, back or abdominal pain, dysuria, hematuria, dependent or periorbital edema
- Changes in blood pressure, body weight, fluid intake, voiding pattern, or urine output
- Concomitant events or procedures such as trauma, surgical procedures, cardiac or hepatic failure, contrast media or other known nephrotoxin administration, or other potential causes of renal dysfunction, e.g., dehydration, hemorrhage, tumor lysis

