
Table 9-5 Follow-up of renal events

Action	Follow up
Assess*, document and record in the Case Report Form (CRF) or via electronic data load. Review and record possible contributing factors to the renal event (co-medications, other co-morbid conditions) and additional diagnostic procedures (MRI etc) in the CRF.	
 • Urine dipstick and sediment microscopy • Blood pressure and body weight • Serum creatinine, electrolytes (sodium, potassium, phosphate, calcium), bicarbonate and uric acid • Urine output
Monitor patient regularly (frequency at investigator's discretion) until:	
 • Event resolution: (sCr within 10% of baseline or protein-creatinine ratio within 50% of baseline) 
or
 
 • Event stabilization: sCr level with $\pm 10\%$ variability over last 6 months or protein-creatinine ratio stabilization at a new level with $\pm 50\%$ variability over last 6 months.

* Urine osmolality: in the absence of diuretics or chronic kidney disease this can be a very sensitive metric for integrated kidney function that requires excellent tubular function. A high urinary osmolality in the setting of an increase in sCr will point toward a “pre-renal” cause rather than tubular toxicity.

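### Renal events are exempted from the related Grade 3 stop and sent to a creatinine discontinuation rule that Section 9.4 does not contain

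*Protocol*

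**What the plan says.** Protocol Section 7.2 lists the events after which study treatment must be discontinued. Three entries matter here.

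- A CTCAE Grade 3 adverse event is a mandatory stop if it is "believed to be related to the study drug (apart from liver and renal events - see below"). Liver and renal events are thus taken out of this rule and given bullets of their own.
- The renal bullet requires a stop for a renal safety event, as defined in Section 9.4, "with serum creatinine elevations mandating study treatment discontinuation".
- A general bullet covers adverse events and abnormal results "that indicate a safety risk to the patient, in the opinion of the investigator".

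Section 9.4 opens its tables with "Recommended actions and follow-up assessments are listed in" Tables 9-4 and 9-5. For a creatinine rise of 50% or more over baseline, Table 9-4 asks for confirmation within 24 to 48 hours. If that is not possible, "study drug must be withheld until further evaluation is possible". It then says "Consider drug interruption" and asks the site to consider hospitalization. Table 9-5 sets out what to assess and record, and then "Monitor patient regularly" until the event resolves or stabilizes.

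For comparison, several rows of the liver table (Section 9.3, Table 9-2) say "Discontinue the study drug immediately" at stated thresholds.

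**The concern.** Section 7.2 takes a rule that works, the related Grade 3 stop, away from renal events and puts in its place a reference to a rule that is not there. A site that follows the protocol exactly finds no grade and no creatinine level at which a patient with a renal event must come off drug.

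What is at stake is the individual patient. Two sites could handle the same confirmed, drug-related severe renal event differently, one stopping drug and one continuing, and both would comply. Section 3.7 names stopping rules among the ways risk is kept down. This is a first-in-patient study (Section 1.1) without a data monitoring committee (Section 10.4), so the written individual rules carry much of the weight.

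**Working it through.** No sample size, power or error rate is involved, so there is no figure of the plan's to reproduce. The check sets Section 7.2 against the tables it points to.

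**Step 1. Look for a creatinine level that mandates discontinuation.** Criteria in Table 9-4:

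| Criterion | Action on study drug | Discontinuation mandated? |
|---|---|---|
| Creatinine up 25–49% | none (confirm, follow up) | no |
| Creatinine up 50% or more (no higher tier) | consider interruption; withhold only if timely confirmation is impossible | no |
| Albumin- or protein-creatinine ratio up 2-fold or more | consider interruption or discontinuation | no |
| Albumin-creatinine ratio at least 30 mg/g, or new dipstick proteinuria | consider interruption or discontinuation | no |
| Protein-creatinine ratio at least 150 mg/g | consider interruption or discontinuation | no |
| New glucosuria not due to diabetes | none | no |
| New hematuria not due to trauma | none | no |

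Result: 0 of 2 creatinine rows and 0 of 7 criteria. If the three albumin/protein lines are one merged row in the source, the total is 7 − 2 = 5 and the count is 0 of 5. Discontinuation is mentioned only for the albumin/protein criteria, and only as something to consider. Table 9-5 contains no discontinuation criterion. Section 9.4 shows no sign of redaction.

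**Step 2. Do the same for the liver bullet.** The 11 rows of Table 9-2:

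- Discontinue outright, 5 rows: potential Hy's Law case; ALT or AST above 8 × ULN (and above 2 × baseline); above 3 × ULN (and above 2 × baseline) with INR above 1.5; above 3 × ULN (and above 2 × baseline) with symptoms; jaundice.
- Discontinue if the elevation persists on repeat, 1 row: isolated total bilirubin above 2 × ULN.
- Referred to Table 6-3, which contains discontinuation steps, 2 rows: the two asymptomatic ALT/AST bands up to 8 × ULN.
- No mandated discontinuation, 3 rows: isolated ALP; bilirubin above 1.5 to 2 × ULN; any adverse event suggesting liver toxicity (consider only).

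Result: 5 + 1 = 6 of 11 rows mandate discontinuation, and 2 more lead to a table that can.

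**Step 3. Follow one patient through the rules.** Take a creatinine rise above 50%, confirmed on time, graded CTCAE 3 and judged related to study drug.

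1. Section 7.2, Grade 3 bullet: does not apply, because the event is renal.
2. Section 7.2, renal bullet: cannot be met, because Section 9.4 contains no mandating elevation.
3. Table 9-4 withhold: does not apply, because the value was confirmed in time.
4. Section 7.5: neither grade-based trigger is met. One needs a related event of Grade 4 or higher; the other needs a similar Grade 3 or higher event in two or more patients.
5. Section 7.2, opinion clauses: the investigator must stop drug if he or she judges that there is a safety risk or that continuing is detrimental.

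Only item 5 can take this patient off drug as a required step, and it sets no threshold.

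**The case against.** The strongest reply is that the Grade 3 stop is not free of judgment either. The site investigator grades severity (Section 7.5) and decides relatedness, and a laboratory abnormality counts as an adverse event only if it causes symptoms, is considered clinically significant or needs therapy (Section 9.1). That is true, and it limits what is claimed: the missing rule is one tied to a grade or threshold, not one free of judgment. Once an event has been graded 3 and called related, however, the stop follows for other organ systems and does not follow for renal events.

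Other safeguards exist. Section 6.6 permits interruption and dose reduction for safety concerns unrelated to ALT/AST. Section 8.6.3 requires clinically relevant laboratory deviations to be discussed with the sponsor and repeated. The sponsor monitors unblinded (Section 6.4), safety reviews are joint (Section 9.7), and patients with eGFR below 60 mL/min are excluded at entry. These help, but none says when a patient must stop, and the stated purpose of Section 6.6 is to let the patient continue. Section 7.5 lets dosing continue during a hold for patients without safety concerns, which implies that the affected patient might not be dosed. That is an implication at study level, not a rule for the patient.

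Three further points stand in part. The liver reference is not perfect: it also names ALP, and the isolated ALP row mandates nothing. The row counts show where rules exist and do not measure risk; more liver rules are to be expected with a drug acting on the liver. Section 3.7's own monitoring example is liver transaminases, so it promises no numeric renal rule. None of this supplies the missing renal stop.

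**Conclusion.** The concern holds and should be fixed. Section 7.2 is wrong as written for renal events: the exemption disables the related Grade 3 stop, and the clause meant to replace it has no content. No creatinine level in Section 9.4 mandates discontinuation (0 of 2 rows), however high the value.

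The conclusion rests on the readable text of Sections 7.2, 7.5 and 9.4 and needs no numerical assumption. It is limited in two ways. Investigator judgment, which makes a stop mandatory once formed, and sponsor oversight reduce the risk. The documents also do not show how often such an event would occur, so no number of affected patients can be given. The point concerns patient safety, not bias in the comparison with placebo.

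**What to change.** Make one of two changes.

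1. In Section 7.2, take renal events out of the exemption, so that a related Grade 3 renal event is a mandatory stop, and remove the reference to a creatinine rule in Section 9.4. The bullet would be better worded as Grade 3 or higher.
2. In Table 9-4, add a confirmed creatinine threshold or a CTCAE grade at which study drug must be discontinued. The documents give no figure for this; the sponsor's safety group should choose it. A creatinine threshold would also be the version least dependent on investigator judgment.

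Under either option it would help to state, in the row for a rise of 50% or more, what happens to study drug once the rise is confirmed.

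The cost is one wording amendment. There are no new tests, visits or patients. A few patients may stop drug earlier than investigator judgment alone would require.

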7.3 Withdrawal of informed consent

Patients may voluntarily withdraw consent to participate in the study for any reason at any time.

Withdrawal of consent from the study is defined as when a patient:

- Does not want to participate in the study anymore and
- Does not want any further visits or assessments and
- Does not want any further study related contacts and
- Does not allow analysis of already obtained biologic material.

In this situation, the investigator must make every effort (e.g. telephone, e-mail, letter) to determine the primary reason for the patient's decision to withdraw his/her consent and record this information.

Study treatment must be discontinued and no further assessments conducted, and the data that would have been collected at subsequent visits will be considered missing.

Further attempts to contact the patient are not allowed unless safety findings require communicating or follow-up.

7.4 Lost to follow-up

For patients whose status is unclear because they fail to appear for study visits without stating an intention to discontinue or withdraw, the investigator should show "due diligence" by documenting in the source documents steps taken to contact the patient, e.g. dates of telephone calls, registered letters, etc. A patient cannot be formally considered lost to follow-up until his/her scheduled end of study visit would have occurred.

7.5 Study Stopping rules

The severity of adverse events will be graded by the study site Investigator (or designee) based on clinical judgment and captured in the CRF AE page. This information will be used to quantify events that may lead to patient's discontinuation or stopping dose arms or the study.

Study Stopping Rules

The study will be placed on hold to further enrollment, no new patients may be dosed, however dosing of those without safety concerns may continue. The study may be stopped based on a full review of all available clinical safety data and discussion with the Investigators if any of the following occur:

- One patient on study drug experiences any adverse event that is CTCAE Grade 4 or higher that is classified as related to study drug.
- Two or more patients on study drug experience a similar adverse event that is a CTCAE Grade 3 or higher other than ALT elevation.
- The Principal Investigator and the Sponsor consider that the number and/or severity of adverse events justify discontinuation of the study.
- The Sponsor unilaterally requests it.

Safety reviews for study stopping will be conducted jointly between medically qualified representatives of the Sponsor and Investigator and a joint decision will be made.

